16.1.8.1. Hypothetical Estimand

The treatment condition of interest is single dose of AZD7442 (two IM injections, one for each mAb component, AZD8895 and AZD1061). The alternative treatment condition to which comparison will be made is a placebo.

The population of participants targeted in the primary estimand includes adults at least 18 years of age who have not had a prior SARS-CoV-2 RT-PCR-positive confirmed COVID-19 infection and who are candidates for benefit from passive immunization with antibodies, defined as having increased risk for inadequate response to active immunization (predicted poor responders to vaccines OR intolerant of vaccine), OR having increased risk for SARS-CoV-2 infection, defined as those whose locations or circumstances put them at appreciable risk of exposure to SARS-CoV-2 and COVID-19.

The primary endpoint (variable) to be obtained is a binary response, whereby a participant is defined as a COVID-19 case if their first case of SARS-CoV-2 RT-PCR-positive symptomatic illness occurs post dose of IMP prior to Day 183.

The population-level summary measure is prophylactic efficacy, calculated as 1 – relative risk (RR). (RR is the incidence of infection in the AZD7442 group relative to the incidence of infection in the control group.)

For participants who become unblinded to treatment assignment and/or take COVID-19 vaccine or other COVID-19 preventive product, in both cases prior to having met the criteria for endpoint, only data prior to the intercurrent event (i.e., up to the date of unblinding/receipt of first dose of COVID-19 preventive product, whichever is earlier) will be considered and data after the intercurrent event will be imputed (i.e., intercurrent events will be handled using hypothetical strategy). A single imputation from the Bernoulli distribution will be used, where the probability that the participant experiences the primary endpoint is the event rate observed in the subset of participants who did not have an intercurrent event in the same arm. The detailed imputation steps are described as follows.

- If the participant experiences a primary endpoint event then no imputation is required, and data is considered up to the Date of Onset of Primary Endpoint (Section 16.1.4).
- If the participant does not experience a primary endpoint event and also has no intercurrent event, then no imputation is performed, and data is considered up to Date of End of Study or Date of Last Assessment, whichever is later. If an end of study date or date of last assessment occurs after Day 183, the efficacy follow-up will be censored at Day 183. For participants who continue to participate in the study at the time of the primary analysis, the DCO date will be used as their last assessment date. For participants with no post-baseline visit data available, the date of IMP administration will be used i.e. follow-up will be 1 day.
- If the participant has an intercurrent event before Day 183 and before a primary endpoint event:
 - O Step 1: The missing event status will then be imputed using a single imputation from the Bernoulli distribution, where the probability that the participant experiences the primary endpoint is the event rate observed in the subset of participants who did not have an intercurrent event in the same arm and age group. For participants in the placebo group: $p_{Placebo} = \frac{E_{Placebo,no \, IE}}{N_{Placebo \, no \, IE}}$, where: $E_{Placebo,no \, IE}$ is the

number of participants in the placebo arm who experience a primary endpoint event and did not experience an intercurrent event; $N_{Placebo,no\ IE}$ is the number of participants in the placebo arm who did not experience an intercurrent event. The value of $p_{Placebo}$ will be calculated separately for each age group within the placebo arm. For participants in the AZD7442 group: $p_{AZD7442} = \frac{E_{AZD7442,no\ IE}}{N_{AZD7442,no\ IE}}$, where: $E_{AZD7442,no\ IE}$ is the number of participants in the AZD7442 arm who experience a primary endpoint event and did not experience an intercurrent event; $N_{AZD7442,no\ IE}$ is the number of participants in the AZD7442 arm who did not experience an intercurrent event. The value of $p_{AZD7442}$ will be calculated separately for each age group within the AZD7442 arm. If there are zero events observed in a given age group in a given arm, then the event rate used for imputation will be the armspecific event rate (pooled across both age groups). The random seed is 23456.

- Step 2: The follow-up time will be calculated as described in Section 16.1.4. For participants who previously had an intercurrent event prior to meeting the primary endpoint and now have an imputed primary endpoint event, the Date of Onset of Primary Endpoint will be the date of the first intercurrent event.
- Step 3: Analyze the complete hypothetical estimand dataset using a Poisson regression model with robust variance as described in Section 16.1.4. Participants with an observed event or an imputed event are both included as events, and participants without an observed event or without an imputed event are no included as primary endpoint events.
- Step 4: Repeat steps 1 through 3 above 100 times. The reported effect size will be the average of the results from the 100 analyses using the imputed datasets.

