16.1.4. PRIMARY ANALYSIS OF PRIMARY EFFICACY ENDPOINT

The primary efficacy analysis of the primary endpoint will be performed on the FPAS. Participants who withdraw from the study prior to having met the criteria for the primary efficacy endpoint will be censored (considered as not having the event) at the time of last observation. Participants with deaths that are caused by SARS-CoV-2 (death related to COVID marked on the death eCRF page) will be considered as having the event, even if no other qualifying symptoms are met. Participants with hospitalizations due to COVID-19 will also be considered as having the event.

A Poisson regression model with robust variance (Zou, 2004) adjusting for follow-up time, will be used as the primary efficacy analysis model to estimate the RR on the incidence of SARS-CoV-2 RT-PCR-positive symptomatic illness occurring post dose of IMP between the AZD7442 and the placebo groups. The model contains the planned treatment group and age group at the time of informed consent (i.e., ≥ 60 years and < 60 years, see Section 7.6) as a covariate. The logarithm of the participant's corresponding follow-up time at risk starting from dose up to the study day 183 visit will be used as an offset variable in the model to adjust for participants having different exposure times during which the events occur. Participants who withdraw or have a non-COVID-19 related death prior to meeting the primary endpoint will not be counted as having the event. The follow up time for those participants will be at that time relative to dose. Calculation of follow-up time is detailed as following:

- For participants who meet the primary endpoint before Day 183, the follow-up time will be calculated as (Date of Onset of Primary Endpoint) (Date of Dosing) + 1. Date of Onset of Primary Endpoint is defined as the assessment date of qualifying COVID symptoms, if associated with a positive SARS-CoV-2 RT-PCR lab test from a sample collected within the 5 days prior to symptom assessment through 10 days after symptom assessment. In the case of death due to COVID-19 or hospitalization due to COVID-19, the Date of Onset of Primary Endpoint is the earliest date of death/date of hospital admission when a qualifying symptom assessment is not observed.
- For participants who do not experience a primary endpoint before Day 183, the efficacy follow-up time will be considered censored and determined based on the following:

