 - o If an end of study date occurs prior to Day 183, the efficacy follow-up time will be calculated as (Date of End of Study or Date of Last Assessment, whichever is later) (Date of Dosing) + 1.
 - o If an end of study date occurs after Day 183, the efficacy follow-up will be censored at Day 183.

For participants who continue to participate in the study at the time of the primary analysis, the DCO date will be used as their last assessment date. For participants with no post-baseline visit data available, the date of IMP administration will be used i.e. follow-up will be 1 day.

Efficacy is the incidence of infection in the AZD7442 group relative to the incidence of infection in the placebo group, expressed as a percentage. Efficacy will be calculated as relative risk reduction (RRR) = 100% x (1 - relative risk).

RRR and its corresponding 2-sided 95% CI will be estimated from the Poisson regression model with robust variance. In addition, the 2-sided p-value testing null hypothesis that there is no difference in efficacy between AZD7442 and placebo (i.e. the efficacy is equal to 0) will be obtained from the model. Statistical significance will be achieved if the lower bound of the 95% CI for efficacy is > 0, which corresponds to an observed two-sided p-value < 0.05. For the final analysis nominal 95% CI's will be presented.

The Poisson regression with robust variance analysis will be implemented by using the SAS PROC GENMOD procedure with the REPEATED statement for participant ID and logarithm link as well as OFFSET option. The estimated parameter $\hat{\beta}$ [i.e., log(RR)], 2-sided 95% confidence interval (CI) for $\hat{\beta}$, and the 2-sided p-value will be obtained from the SAS outputs. The estimated RR and corresponding CI for the RR is given by exponentiating $\hat{\beta}$ and its confidence limits. Therefore, the percent of RRR is given by $[(1 - \exp(\hat{\beta})) * 100\%]$. The CI for the percent of RRR is given by ([1 - exp(upper confidence limit for $\hat{\beta}$) * 100%], [1 - exp(lower confidence limit for $\hat{\beta}$) * 100%]).

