16.1.5. SENSITIVITY ANALYSES FOR PRIMARY EFFICACY ENDPOINT

As a sensitivity analysis to the handling of missing data in the analysis of the primary efficacy endpoint, the primary analysis of the primary efficacy endpoint (Section 16.1.4) will be repeated with multiple imputation for intercurrent events. For participants who are in FPAS but (1) do not have a SARS-CoV-2 RT-PCR-positive symptomatic illness status occurring post dose of IMP and withdraw from the study prior to the time of analysis, or (2) were unblinded to treatment assignment prior to having met the criteria for the primary efficacy endpoint, or (3) received COVID-19 vaccine or other preventive product prior to having met the criteria for the primary efficacy endpoint, their event status will be imputed assuming the observed event rate per treatment group conditional on stratification factors using multiple imputation techniques as described in the following paragraphs.

The primary analysis using Poisson regression with robust variance requires a participant-level dataset. A repeated imputation approach is introduced to impute the status of SARS-CoV-2 RT-PCR-positive symptomatic illness occurring post dose of IMP for missing observations at the participant level for the model fitting. By incorporating the between-imputation variance, a reliable statistical inference in both hypothesis testing and CI estimation of the treatment effect is expected through the repeated imputation (Little and Rubin, 2002). In the primary analysis the missing outcome for participants who drop out (e.g., withdrawal, lost to follow-up, death not caused by SARS-CoV-2, etc.) prior to reaching cut-off time for analysis without a SARS-CoV-2 RT-PCR-positive symptomatic illness occurring post dose of IMP will be imputed per stratum determined by the stratification factor using observed event rate per treatment group. The imputation and subsequent analysis may be carried out using SAS PROC MI (Monotone Logistic Regression Method) and SAS PROC MIANALYZE. The detailed imputation steps are described as follows.

- Step 1: Missing events in both arms will be imputed with the observed event rate per treatment group. The imputation may be executed using SAS PROC MI (logistic regression method with the recoded treatment term and stratification factor), or random sampling from an appropriate distribution. The random seed is 10021.

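### Two supportive analyses (SAP 16.1.8.1 and 16.1.5) impute intercurrent-event participants with no allowance for time already survived, which biases efficacy if the share of such participants differs by arm; 16.1.8.1 also lacks a variance rule

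*SAP*

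**What the plan says.** The SAP covers the parent PROVENT trial. Its primary estimand (16.1.3) censors a participant at an IE that precedes the endpoint.

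**16.1.8.1, hypothetical estimand.** The lead-in concerns IEs "in both cases prior to having met the criteria for endpoint, only data prior to the intercurrent event" being used; what follows is imputed.

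- Step 1: the probability of an event "is the event rate observed in the subset of participants who did not have an intercurrent event in the same arm and age group", written as E/N. For placebo, E is the "number of participants in the placebo arm who experience a primary endpoint event and did not experience an intercurrent event"; the active arm is treated alike.
- Step 2: follow-up comes from 16.1.4. For an imputed event, "the Date of Onset of Primary Endpoint will be the date of the first intercurrent event".
- Step 3: the 16.1.4 Poisson model is refitted. There the log of follow-up time "will be used as an offset variable in the model to adjust for participants having different exposure times". The 16.1.4 follow-up rules have no line for an IE; for non-events they say "If an end of study date occurs after Day 183, the efficacy follow-up will be censored at Day 183", or stop at data cut-off for participants still in the study.
- Step 4: "The reported effect size will be the average of the results from the 100 analyses using the imputed datasets". Nothing is said about variance or a confidence interval.

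**16.1.5, sensitivity analysis.** This repeats the 16.1.4 analysis with multiple imputation. It covers withdrawals, those who "2) were unblinded to treatment assignment prior to having met the criteria for the primary efficacy endpoint", and those who took a preventive product. Events are drawn at the observed rate by arm and stratum, with no term for time. Twenty datasets are pooled with PROC MIANALYZE.

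Neither analysis is in the section 7.4 hierarchy, which runs: primary, treatment policy (Table O), all-cause death (Table P), key secondary.

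**The concern.** A participant with an IE is known to have been event-free up to it. Only the time after the IE is unknown, so only that time should carry imputed risk. Step 1 instead assigns the risk of the whole observed period, and Step 2 dates the imputed event at the IE. Time already survived is charged with risk twice, and each arm's event rate is inflated.

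If the inflation is the same in both arms it cancels in the relative risk. If one arm has more IEs it does not, and estimated efficacy shifts for a reason unrelated to the drug. Both analyses are there to show whether the primary result is robust to IEs. A shift of this kind could be read as a warning or as reassurance when it is neither. IEs are not expected to be marginal: SAP 4.4 makes unblinding of 30% of participants a trigger for the primary analysis.

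**Working it through.** **1. The plan's own figure.** The SAP gives no figure for these two analyses. Its only related figure is the power in Table L (SAP 7.1). With 3433 vs 1717 participants and 80% efficacy, the active share of events is 3433×0.2/(3433×0.2+1717) = 686.6/2403.6 = 0.286. An exact binomial split of the fixed event total, with a Wald test on log RR and variance 1/a − 1/3433 + 1/b − 1/1717, gives power of 88.8, 96.5, 97.3 and 97.8% at 18, 20, 22 and 24 events. Table L has 89, 96, 97 and 98%. It is reproduced, and nothing below changes it.

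**2. Inputs.** True efficacy 80% (SAP 7.1). The overall IE share is taken as 30%, from the trigger in SAP 4.4. Shares by arm are assumptions that keep 30% overall at 2:1: 25% active/40% placebo, since (2×25+40)/3 = 30, and 36%/18%, since (2×36+18)/3 = 30. IE times are assumed exponential and the event hazard constant and low. The period is set to 1.

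**3. Inflation factor in one arm.** Let λ be the event risk over the period, s the IE share and m the mean IE time among those with an IE. Real events before any IE number λ(1−s+sm) per participant.

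- If E counts cases whose IE came later, E/N = λ(1−s+sm)/(1−s). Real plus imputed events are then λ(1−s+sm)/(1−s).
- If E drops those cases, E/N = λ. The total is then λ(1+sm).
- Person-time is 1 if imputed non-events run to the end of the period, and 1−s+sm if follow-up stops at the IE.

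Dividing events by person-time and by λ gives four factors. Reported RR = 0.2 × active factor / placebo factor. The exponential assumption gives m = 0.476 (s=0.25), 0.458 (0.40), 0.463 (0.36) and 0.483 (0.18).

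| Reading | Factor | 25/40 | 36/18 | 30/30 |
|---|---|---|---|---|
| A: E counts later-IE cases, follow-up to end | 1+sm/(1−s) | 82.2% | 77.2% | 80.0% |
| B: E drops them, follow-up to end | 1+sm | 81.1% | 78.5% | 80.0% |
| C: E counts them, follow-up stops at IE | 1/(1−s) | 84.0% | 74.4% | 80.0% |
| D: E drops them, follow-up stops at IE | (1+sm)/(1−s+sm) | 83.0% | 75.9% | 80.0% |

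Example, reading C at 25/40: (1/0.75)/(1/0.60) = 0.80; RR = 0.16; efficacy 84.0%.

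Simulation (3433 vs 1717, 24 expected events before any IE, 3,000 trials, 100 imputations, no age strata) gave medians, A to D, of 82.3, 81.1, 84.0 and 82.9% at 25/40, and 77.8, 79.0, 75.1 and 76.5% at 36/18.

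**4. Section 16.1.5.** For IE participants the observed rate is the first E/N above, so the factor is A if follow-up runs to the end (or no offset is used) and C if it stops at the IE. Withdrawals are left out of this check.

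**5. Timing alone.** With 30% in each arm and mean IE time 0.50 on active and 0.25 on placebo, A to D give 78.1, 78.6, 80.0 and 80.5%. Under C the factor contains no m, so timing has no effect.

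**6. Interval.** The SAP does not say that standard errors are averaged. If they were, simulated 95% coverage at 30/30 would be 0.908–0.925, against 0.952–0.956 with Rubin pooling. At true efficacy 80% the mean averaged standard error of log RR was 0.407–0.417, while the estimates had a standard deviation of 0.501–0.504.

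**7. Remaining-time imputation.** With a gamma-drawn rate per person-time, remaining time only and Rubin pooling, medians were 80.0–80.6% and coverage 0.957–0.966 over the share and timing scenarios.

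**The case against.** The strongest reply is that little depends on this. Both analyses are outside the hierarchy, and treatment policy, inside it, already tests sensitivity to IEs. The shift is also modest beside sampling error. On the log scale it runs from |ln(0.9457)| = 0.06 (reading B, 25/40) to ln(1.281) = 0.25 (reading C, 36/18). The interval of 46 to 90% reported in Protocol 2.3.2 implies a standard error of about [ln(0.54) − ln(0.10)]/3.92 = 0.43, so the shift is about 0.1 to 0.6 standard errors. All of this stands, and it limits the weight of the point. It does not make the imputation rule correct.

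A reader might infer more than the documents support in four places:

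- **Timing differences always bias 16.1.8.1.** They do not. If its lead-in governs both E and follow-up, and follow-up stops at the IE (reading C), only the share matters.
- **E/N is a 183-day risk.** At the primary analysis, follow-up of ongoing participants ends at data cut-off, so it is a proportion over the observed period.
- **16.1.5 drops the offset.** Its Step 3 lists only treatment and the stratification factor, but the section opens by repeating the 16.1.4 analysis, which has the offset. This needs a clarifying line only.
- **The while-on-treatment estimate is an unbiased yardstick.** That needs a near-constant hazard. With a hazard rising linearly from zero, each arm's rate is proportional to 2m; falling to zero, to 2(1−m). The 25/40 and 36/18 cases then give 79.2–80.8%.

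The definition of E is likewise a clarification: the lead-in concerns only IEs before the endpoint, which implies that cases with a later IE belong in E.

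**Conclusion.** The point holds for the two supportive analyses only. As written, 16.1.8.1 and 16.1.5 assign IE participants an observed-period risk regardless of time already survived. At true efficacy 80% the hypothetical estimate becomes about 81–84% with IE shares of 25% active/40% placebo and about 74–79% with 36%/18%. It is unbiased when share and timing are equal. These sizes rest on assumed IE shares, exponential IE times, a constant hazard and non-informative IEs; the documents give no shares or timing by arm, so neither the direction nor the size in this trial can be stated.

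The missing variance rule in 16.1.8.1 is a plain gap, since 16.1.5 has one. It would be too strong to say that the planned interval undercovers: no interval is defined, and the low coverage above applies only if standard errors were averaged. Nothing here calls the primary test, Table L or the section 7.4 hierarchy into question. The change should be made.

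**What to change.** In 16.1.8.1, and for IE participants in 16.1.5:

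- Impute from the arm- and age-specific event rate per person-time, drawn with its uncertainty, over the time from the IE to Day 183 or data cut-off.
- Place imputed onset within that time, and follow imputed non-events to its end.
- State once that cases whose IE came after the endpoint count in E.
- State in 16.1.5 Step 3 that the 16.1.4 offset is kept.
- Pool log RR and its variance with PROC MIANALYZE in both sections, and report that interval.

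The cost is SAP wording and modest programming. The interval for the hypothetical estimand will probably be wider. The estimate will lie close to the while-on-treatment result (mean log RR within 0.015 and correlation 0.999 in simulation), because both assume non-informative IEs and a roughly constant hazard. Treatment policy (Table O) therefore stays the main check on IEs. Protocol 2.3.2 reports the primary analysis as done, so any rerun must be labelled post hoc.

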16.1.9. KEY SUPPORTIVE ANALYSES OF PRIMARY EFFICACY ENDPOINT

As key supportive analyses, the primary analysis of the efficacy endpoint (refer to Section 16.1.4) will be repeated using two key supportive estimands: one, which utilizes a treatment policy strategy for intercurrent events, and a second, which includes death due to any cause in the primary endpoint. These analyses are included in the multiple testing hierarchy described in Section 7.4. The attributes of the key supportive estimands are described in Table O: and Table P:.

Table O: List of First Key Supportive Estimand Attributes

Label	The efficacy of a single IM dose of AZD7442 compared to placebo for the prevention of COVID-19 prior to Day 183 – Treatment Policy Estimand
Definition	Full pre-exposure analysis set, defined as all participants who were randomized, received
Population	at least one of the planned injections of IMP, and did not have a prior SARS-CoV-2 RT-
	PCR-positive confirmed COVID-19 infection. Targeted participants will have the
	following characteristics:
	Adults ≥ 18 years of age who are candidates for benefit from passive immunization with
	antibodies, defined as having increased risk for inadequate response to active
	immunization (predicted poor responders to vaccines OR intolerant of vaccine), OR

	having increased risk for SARS-CoV-2 infection, defined as those whose locations or circumstances put them at appreciable risk of exposure to SARS-CoV-2 and COVID-19.
Treatment Condition of Interest	Single dose of AZD7442 (× 2 IM injections, 1 for each mAb component) or placebo
Variable/Endpoint	A binary response, whereby a participant is defined as a COVID-19 case if their first case of SARS-CoV-2 RT-PCR-positive symptomatic illness occurs post dose of IMP and prior to Day 183.
Intercurrent event handling strategy	Participants who become unblinded to treatment assignment and/or take COVID-19 vaccine or other COVID-19 preventive product, in both cases prior to having met the criteria for the primary efficacy endpoint, will be included and analyzed regardless (i.e., intercurrent events will be handled using a treatment policy strategy).
Population-level summary measure	Prophylactic efficacy, calculated as 1-relative risk. (Relative risk is the incidence of infection in the AZD7442 group relative to the incidence of infection in the control group.)

Table P: List of Second Key Supportive Estimand Attributes

Label	The efficacy of a single IM dose of AZD7442 compared to placebo for the prevention of COVID-19 prior to Day 183 – All-Cause Mortality Estimand
Definition Population	Full pre-exposure analysis set, defined as all participants who were randomized, received at least one of the planned injections of IMP, and did not have a prior SARS-CoV-2 RT-PCR-positive confirmed COVID-19 infection. Targeted participants will have the following characteristics: Adults ≥ 18 years of age who are candidates for benefit from passive immunization with antibodies, defined as having increased risk for inadequate response to active immunization (predicted poor responders to vaccines OR intolerant of vaccine), OR having increased risk for SARS-CoV-2 infection, defined as those whose locations or circumstances put them at appreciable risk of exposure to SARS-CoV-2 and COVID-19.
Treatment Condition of Interest	Single dose of AZD7442 (× 2 IM injections, 1 for each mAb component) or placebo
Variable/Endpoint	A binary response, whereby a participant is defined as a COVID-19 case if their first case of SARS-CoV-2 RT-PCR-positive symptomatic illness or death from any cause occurs

	post dose of IMP and prior to Day 183.	
Intercurrent event	Participants who become unblinded to treatment assignment and/or take COVID-19	
handling strategy	vaccine or other COVID-19 preventive product, in both cases prior to having met the	
	criteria for the primary efficacy endpoint, will be censored at the date of	
	unblinding/receipt of first dose of COVID-19 preventive product, whichever is earlier	
	(i.e., intercurrent events will be handled using a while on treatment strategy).	
Population-level	Prophylactic efficacy, calculated as 1-relative risk. (Relative risk is the incidence of	
summary measure	infection in the AZD7442 group relative to the incidence of infection in the control	
	group.)	

